6.1.1 Transfusion from Week 5 to EOETP Primary Analysis Set

The transfusion from week 5 to EOETP primary analysis set will include all subjects in the primary analysis set whose EOETP is \geq day 29. The analysis of the endpoint of transfusion or hemoglobin \leq 8.0 g/dL from day 29 to EOETP will be performed using this primary analysis set.

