10. STATISTICAL CONSIDERATIONS

10.1 Study Design

This is a double-blind, randomized, placebo-controlled, phase 3 non-inferiority study in CIA subjects receiving multi-cycle chemotherapy for the treatment of stage IV NSCLC cancer. Randomization will occur in a 2 to 1 ratio (darbepoetin alfa to placebo) and will be stratified by geographic region, histology (squamous versus other), and screening hemoglobin (< 10.0 g/dL versus \ge 10.0 g/dL). Subjects will receive IP Q3W during the treatment period. IP will be discontinued within 3 weeks after the last dose of chemotherapy, or upon the determination of disease progression, whichever occurs first. Study visits Q3W and imaging studies Q9W will occur during the treatment period until disease progression. The EOTP visit will occur at the next Q3W visit after disease progression has been determined. Subjects will then enter long-term follow-up and will be followed for survival until death, or until approximately 2700 deaths have occurred.

The primary objective of the study is to demonstrate that subjects treated with darbepoetin alfa to a hemoglobin ceiling of 12 g/dL is non-inferior to subjects on placebo with respect to survival. Key secondary objectives include demonstrating that subjects treated with darbepoetin alfa to a hemoglobin ceiling of 12 g/dL is non-inferior to subjects on placebo with respect to PFS and demonstrating that darbepoetin alfa is superior to placebo with respect to transfusions.

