10.3 Sample Size Considerations

A total of 2700 deaths will be observed in order to exclude a hazard ratio (darbepoetin alfa to placebo) of 1.15 with a 1-sided significance level of 0.025. With 2700 deaths, the study is powered at just over 90% if the true hazard ratio is 1.0 (approximately, 93%). To observe 2700 deaths, the study will randomize a total of 3000 subjects which assumes a 7-year enrollment period, a 3-year follow-up after last subject enrolled, a 1-year survival rate of 51% (Sandler et al, 2006), and a common exponential drop-out rate of 0.0511.

Excluding a hazard ratio of 1.15 corresponds to excluding a decrease in median survival of approximately 1.6 months in the darbepoetin alfa arm group compared to placebo.

This estimation assumes survival time is exponentially distributed which allows for a conversion from a hazard ratio to medians. A median survival of 12.3 months (Sandler et al, 2006) was assumed as the median survival in the placebo arm in order to derive the difference in medians that correspond to a hazard ratio of 1.15.

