10.6.2.2 Analysis of Secondary Endpoints

The same method used to analyze OS will be used to analyze PFS. Progression-free survival will be measured from randomization to disease progression (as defined by the version of RECIST specified in the protocol at the time of subject enrollment using investigator-assessed scans) or death from any cause; subjects without either event will be censored at the last disease assessment date. Non-inferiority will be declared if the upper confidence limit for the hazard ratio is less than 1.15 using a 1-sided significance level of 0.025. This analysis will be performed on all subjects in the primary analysis set who have not had disease progression prior to randomization.

If non-inferiority is declared for both OS and PFS, then the effectiveness of darbepoetin alfa in reducing the incidence of RBC transfusions or a hemoglobin ≤ 8.0 g/dL will be formally tested. To assess treatment group differences, a 2-sided Cochran-Mantel-Haenszel test at a significance level of 0.05 will be used which will adjust for the stratification factors at randomization. The incidence will be assessed from day 29 to the EOETP. This analysis will be performed on all subjects in the primary analysis set whose EOETP is \geq day 29.

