		9.6.4	Adverse Events and Disease-related Events	40
		9.6.5	Laboratory Test Results	41
		9.6.6	Vital Signs	42
		9.6.7	Physical Measurements	42
		9.6.8	Electrocardiogram	42
		9.6.9	Antibody Formation	42
		9.6.10	Exposure to Investigational Product	42
		9.6.11	Exposure to Other Protocol-specified Treatment	43
		9.6.12	Exposure to Concomitant Medication	43
10.	Chan	ges From	Protocol-specified Analyses	45
11.	Litera	ture Citati	ons / References	46
12.	Priorit	ization of	Analyses	47
13.	Data I	Not Cover	red by This Plan	48
14.	Apper	ndices		49
	Apper	ndix A. Te Procedu	echnical Detail and Supplemental Information Regarding Statisti Ires and Programs	cal 49
	Apper	ndix B. Co	oncomitant Medications	52

List of Table

Table 9-1.	Efficacy Endpoint Summary Table	25
Table 9-2.	Safety Endpoint Summary Table	30

List of Abbreviations and Definition of Terms

Abbreviation or Term	Definition/Explanation
AE	Adverse Event
ATE	Arterial thromboembolic event
Baseline Value	The baseline value is the value measured on study day 1 before the first dose of investigational product. If such a measurement is not available, the closest value measured within 7 days before randomization/ study day 1 will be used as the baseline value. For assessments not scheduled to be performed on study day 1, the baseline value is the value from the screening period measured closest to study day 1.
	The definition above will be used to derive "baseline" hemoglobin but it should be noted that the "screening" hemoglobin is the value taken just prior to randomization to determine eligibility and randomization stratum; and the "pre-chemotherapy" hemoglobin is the value taken just prior to the start of first line chemotherapy for NSCLC. It should also be noted that "baseline" in terms of imaging studies will be defined as the imaging studies performed just prior to the start of first line chemotherapy for NSCLC.
CIA	Chemotherapy-induced anemia
CTCAE	Common Toxicity Criteria for Adverse Events
DMC	Data monitoring committee
ECOG	Eastern Cooperative Oncology Group
eCRF	Electronic case report form
EDC	Electronic data capture
End of the Efficacy Treatment Period	End of the efficacy treatment period is defined as 21 days after either the last dose of IP or the last dose of chemotherapy, whichever is later; the EOETP will be set to the EOTP if the EOETP exceeds the EOTP

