8.3.3 Missing Transfusion Data

Subjects who withdraw from study prior to day 29 will have missing data for the secondary endpoint, "RBC transfusion or hemoglobin \leq 8.0 g/dL from week 5 (day 29) to EOETP"; these subjects will be excluded from the analysis of this endpoint.

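### The day 29 transfusion analysis set has no alive-at-day-29 condition, so some subjects who die before day 29 would enter it as event-free with no time at risk; the expected bias is small and the repair is cheap.

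*SAP*

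**What the plan says.** The endpoint is at least one RBC transfusion or a hemoglobin of 8.0 g/dL or less. Protocol 10.6.2.2 sets the window: "The incidence will be assessed from day 29 to the EOETP". The SAP list of definitions fixes its end: "End of the efficacy treatment period is defined as 21 days after either the last dose of IP or the last dose of chemotherapy". Of the two doses the later one counts, and the date is reduced to the EOTP if that comes first. EOTP is the Q3W visit after progression, or the next Q3W visit for a subject who cannot continue visits and imaging.

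SAP 6.1.1 sets the analysis set, which "will include all subjects in the primary analysis set whose EOETP is" day 29 or later. It has no other condition beyond membership of the primary analysis set. SAP 8.3.3 adds: "Subjects who withdraw from study prior to day 29 will have missing data for the secondary endpoint", and excludes them.

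Death appears in none of these rules. The SAP does use date of death in its definition of end of study, but EOETP is capped at EOTP, not at end of study. In SAP 4.2, withdrawn subjects and subjects who died are listed as separate groups, which suggests that withdrawal in 8.3.3 does not include death.

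**The concern.** The set is meant to hold subjects who can be observed from day 29. A date computed forward from the last dose does not guarantee that, because it can fall after the subject has died. Such a subject adds to the denominator, cannot add to the numerator, and is scored as a success. A subject in the set who dies after day 29 without an event is also scored as a success, although the remaining window was never observed.

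This endpoint is the third step of the confirmatory hierarchy, tested by a two-sided CMH test at 0.05. The trial was started because ESAs may raise mortality, and Protocol 2.3 justifies the survival margin by weighing it against fewer transfusions. The benefit side of that comparison should not gain from deaths. The sensitivity analyses in SAP 9.5.2 and Table 9-1 cover transfusion alone, transfusion at hemoglobin of 8.0 g/dL or less, stratification factors, a logistic model, early termination and delayed start. None concerns death.

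**Working it through.** **The plan's own figures first.** The documents give no power or event rate for the transfusion endpoint, so the check is on the survival assumptions. Protocol 10.3 states "A total of 2700 deaths will be observed in order to exclude a hazard ratio"; the ratio to be excluded is 1.15, at a one-sided level of 0.025, and power is put at about 93% for a true hazard ratio of 1.0. Allocation is 2:1 (Protocol 10.1).

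- SE(log HR) = sqrt(9 / (2 × 2700)) = 0.0408.
- Power = Φ(ln 1.15 / 0.0408 − 1.96) = Φ(1.463) = 92.8%. This reproduces.
- Hazard from 51% 1-year survival: −ln(0.51) = 0.673 per year. With drop-out 0.0511 per year (total s = 0.724), 7 years of uniform accrual and 3 of follow-up, expected deaths = 3000 × (0.673/s) × [1 − (exp(−3s) − exp(−10s))/(7s)] = 2726, close to 2700.

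**Who enters the set.** EOETP = last dose day + 21, with no EOTP before day 29:

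| Last IP or chemotherapy dose | EOETP | In set (≥ 29) |
|---|---|---|
| day 1 | 22 | no |
| day 7 | 28 | no |
| day 8 | 29 | yes |
| day 22 | 43 | yes |

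So a last dose on day 8 or later is enough, whether or not the subject is alive on day 29. SAP Appendix A puts IP dose 2 at day 22 (window 15-27).

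**How many.** With daily hazard λ = 0.673/365.25 = 0.001844 and S(d) = exp(−λ(d − 1)):

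| Hazard | Die days 22-28: S(22) − S(29) | Die days 8-28: S(8) − S(29) |
|---|---|---|
| planned | 1.2% (37 of 3000; 31 of 2549) | 3.7% (112 of 3000; 96 of 2549) |
| half (assumed) | 0.6% (19 of 3000) | 1.9% (57 of 3000) |
| quarter (assumed) | 0.3% (10 of 3000) | 1.0% (29 of 3000) |

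These are upper bounds at each hazard. The first column assumes that all of these subjects had a dose on day 8 or later (for example the second IP dose), the second that every one had IP or chemotherapy on day 8 or later, and both assume no EOTP before day 29. The lower hazards allow for the inclusion criterion of life expectancy above 6 months.

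**Effect on the odds ratio, no true treatment effect.** Let both arms have the same event hazard h, death hazard m, and a window of W days. The incidence with deaths scored as non-events is F = h/(h + m) × (1 − exp(−(h + m)W)). Assume a 30% event probability without death and W = 98, so h = −ln(0.7)/98 = 0.00364.

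- Placebo, m = 0.001844: F = 0.2759.
- Darbepoetin, m × 1.15: F = 0.2726.
- Odds ratio = (0.2726/0.7274) / (0.2759/0.7241) = 0.983.

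Across event probabilities of 20-40%, W of 56-98 days, and with or without deaths on days 22-28 counted in the set (F multiplied by exp(−7m)), the odds ratio is 0.979-0.991 at death HR 1.15 and 0.958-0.982 at 1.3. At 1.0 it is exactly 1.

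**Effect with a true difference.** Take 30% against 20% (odds ratio 0.583). Adding 1.3-3.8% zero-exposure deaths equally to both arms gives 0.585-0.587, slightly toward the null. With the darbepoetin share multiplied by 1.15 the odds ratio stays at 0.583.

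**What the gate allows.** The test is formal only after OS and PFS non-inferiority. At 2700 deaths, an upper limit below 1.15 needs an observed OS HR of at most exp(ln 1.15 − 1.96 × 0.0408) = 1.06. The same formula for F with death HR 1.06 gives odds ratios of 0.991-0.996.

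**The case against.** The strongest reply is that the gate and the arithmetic leave little to correct. A confirmatory transfusion claim requires an observed OS hazard ratio of about 1.06 or less (lower still with fewer deaths after early termination), and there the shift in the odds ratio is below 0.01. This stands, unless early deaths are more unbalanced than deaths overall.

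Second, capping EOETP at death changes nothing after day 29, because nothing can be recorded after death. This also stands. The cap repairs only deaths before day 29. For later deaths the question is one of estimand: incidence with death scored as a non-event is a legitimate pre-specified quantity, and only a sensitivity analysis can show how much death drives it.

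Third, a reader might infer that SAP 6.1.1 and 8.3.3 contradict each other for early withdrawals. They need not: 6.1.1 forms the set and 8.3.3 then removes withdrawals before day 29. A cross-reference would suffice. Death is the case that neither section covers.

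Fourth, sites may record the death date as the EOTP date, which would close the early-death gap. The documents do not say so.

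**Conclusion.** The gap is real and of minor consequence. As written, the inclusion rule admits subjects who died before day 29 if their last dose was on day 8 or later and they have no EOTP date before day 29. At most about 1.2% to 3.7% of subjects are affected at the planned hazard, and about half that or less if early mortality is lower. The bias runs toward the arm with more deaths. With no true effect it is an odds ratio of about 0.98-0.99 at death HR 1.15, and nearer 1 at hazard ratios that pass the OS gate. Event probabilities, window lengths and the reduced early hazards are assumptions.

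Two stronger readings are not supported. A reader might infer that every later death without an event is scored a success. That holds only inside the set: subjects last dosed before day 8, or with an EOTP before day 29, are not in it, and deaths after EOETP fall outside the window. A reader might also multiply the death risk over the window by 0.15 and call the result bias. That counts extra deaths, including subjects who already had an event or never would have. It also treats the window as fixed, although it ends 21 days after the last dose or at EOTP. This issue alone is unlikely to reverse a clear transfusion result.

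**What to change.** - **SAP 6.1.1:** require the subject to be alive and on study at day 29, in addition to EOETP on or after day 29. For set membership, capping EOETP at death, withdrawal or last contact does the same.
- **SAP 8.3.3:** extend the exclusion to death before day 29 and cross-reference it to 6.1.1.
- **SAP 9.5.2:** add one sensitivity analysis that counts death between day 29 and the dose-based EOETP as an event, or treats death as a competing event in a time-to-first-event analysis. If EOETP is capped at death, keep the uncapped date for this analysis.

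All dates needed are already collected. The cost is SAP wording, one extra table, a slightly smaller analysis set and a slightly higher reported incidence.

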6.1.2 Full Analysis Set

The full analysis set will include all randomized and consented subjects. Subjects will be analyzed according to their randomized treatment group. A sensitivity analysis of overall survival will be performed using the full analysis set.

6.1.3 Radiographic Endpoint Primary Analysis Set

The radiographic endpoint primary analysis set will include all randomized and consented subjects who have not had disease progression prior to randomization and who received at least one dose of investigational product. Subjects will be analyzed according to their randomized treatment group.

6.1.4 Radiographic Endpoint Full Analysis Set

The radiographic endpoint full analysis set will include all randomized and consented subjects who have not had disease progression prior to randomization. Subjects will be analyzed according to their randomized treatment group. This data set will be used as a sensitivity analysis for progression-free survival.

6.2 Safety Analysis Set

The safety analysis set will include all randomized and consented subjects who receive at least one dose of investigational product. Subjects will be analyzed according to their actual treatment group. If a subject is randomized to placebo but receives at least 1 dose of darbepoetin alfa, then that subject will be analyzed as a darbepoetin alfa subject. If a subject

is randomized to darbepoetin alfa but only receives placebo, then that subject will be analyzed as a placebo subject. The safety analysis set will be used to analyze adverse events, VTEs, hematologies, chemistries, dosing, vital signs, and antibody data.

6.3 Per Protocol Sets

Since poor adherence to the protocol could have the potential to bias the results towards a conclusion of non-inferiority, a sensitivity analysis will be performed on a per protocol set to confirm results from the primary analysis set. The sensitivity analysis using this per protocol set will be performed for overall survival and **progression free survival**. The per protocol set will include subjects in the primary analysis set who meet all of the following additional criteria **(also see Appendix A):**

- had metastatic (Stage IV) or advanced stage IIIB with malignant pleural effusion (prior to Amendment 3) NSCLC
- no disease progression prior to study day 1
- no history of or current cancer diagnosis other than NSCLC
- had baseline pre-chemo scan prior to randomization (for PFS only)
- had an ECOG performance status of 0 or 1 at screening
- had a life expectancy > 6 months based on the judgment of the investigator at screening
- did not receive erythropoiesis stimulating agents within the 28 days prior to screening
- did not have a documented history of pure red cell aplasia
- dosed per protocol through week 7 with the correctly assigned investigational product (this includes receiving planned doses and dose adjustments per section 6.1.2 of the protocol)
- received first-line cyclic chemotherapy for NSCLC during the treatment period
- did not receive erythropoiesis stimulating agents, other than investigational product as defined in the protocol, during the treatment period.

6.4 Interim Analyses Set(s)

The interim analyses will be conducted on subjects in primary analysis set who are in the clinical trial database at the time of the interim analyses. **The interim analysis may include subjects with only partial data** (eg, a subject may have only been on study through week 3).

7. Planned Analyses

7.1 Interim Analysis and Early Stopping Guidelines

An Independent Biostatistics Group (IBG) will perform regular safety and interim analyses for an independent Data Monitoring Committee (DMC). The DMC will review all available safety data regularly; once every 6 months for the first 2 years and once a year thereafter. In addition, the IBG will conduct 5 formal interim analyses to assess harm (ie, inferiority of darbepoetin alfa relative to placebo) which will occur when approximately 10%, 20%, 30%, 40% and 60% of the planned total of 2700 deaths have been observed. If warranted from these reviews, the DMC may request additional safety data, recommend modifying or stopping the treatment, or recommend suspending randomization. In addition, the DMC will review enrollment status and assess changes in the practice of medicine to make recommendations regarding the ongoing feasibility of the trials.

The IBG and DMC will have access to subjects' individual treatment assignments. To minimize the potential introduction of bias to the conduct of the study, members of the DMC and will not have any direct contact with study center personnel or subjects. The DMC will communicate major safety concerns and recommendations regarding study modification or termination based on the safety parameters to Amgen in accordance with the DMC charter.

Records of all meetings will be approved by the DMC and maintained by the IBG on behalf of the DMC Chair for the duration of the study. Records of all meetings will be transferred and archived in the eTMF (in accordance with SOP-024846) at the conclusion of the study. Further details are provided in the DMC charter.

7.2 Primary Analysis

The primary analysis will be triggered by the study termination date. The **planned** study termination date will be the date when the 2700th death is reported in the clinical trial database **or the study is otherwise stopped**. The study was terminated early based on an independent Data Monitoring Committee recommendation. The study was closed to further enrollment as of 8 May 2017. Sites were instructed to enter all outstanding data into the clinical trial database as of 7 June2017, the database will be cleaned, a snapshot will be taken, the database will be locked, and the primary analysis will be performed. Any additional deaths reported during the entry of outstanding data which occur on or prior to the termination date will be counted in the primary analysis. The primary analysis will also serve as the final analysis for this study.

8. Data Screening and Acceptance

8.1 General Principles

The objective of the data screening is to assess the quantity, quality, and statistical characteristics of the data relative to the requirements of the planned analyses.

8.2 Data Handling and Electronic Transfer of Data

The Amgen Global Study Operations-Data Management (GSO-DM) department will provide all data to be used in the planned analyses. This study uses the RAVE database.

8.3 Handling of Missing and Incomplete Data

8.3.1 Missing Survival Data

Subjects who did not die on study and are lost to follow-up will be censored on the date last known to be alive.

8.3.2 Missing Progression Data

In order to minimize missing progression data, the study is designed to follow subjects until documented radiographic disease progression. If radiographic disease progression is not observed, the primary analysis **of progression-free survival and time to progression** will censor subjects at their last on-study disease assessment date.

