Cerebrovascular disorders	Central nervous system vascular	Narrow
	disorders SMQ	
Hypertension	Hypertension SMQ	Narrow
Cardiac failure	Cardiac failure SMQ	Narrow
Thromboembolic events, venous	Embolic and thrombotic events,	Narrow
	venous	
Convulsions	Convulsions SMQ	Narrow & Broad
Severe cutaneous reactions	Severe cutaneous reactions SMQ	Narrow & Broad
Hypersensitivity	Hypersensitivity SMQ	Narrow & Broad
PRCA	Antibody-mediated Pure Red Cell Aplasia AMQ	

Events of Interest (EOI): EOIs for Aranesp are as follows:

Hemoglobin Threshold

A hemoglobin that increases to >12 g/dL at any time during the treatment period is considered to have exceeded the threshold. This increase will be summarized both by including and excluding hemoglobin values that occurred in the 28-day period following an RBC transfusion.

Medications of Interest (MOI): MOIs for Aranesp Oncology are as follows based on values as of **Q2 2017** or later:

Antihypertensives
Antimicrobials
Antithrombotic agents
Colony stimulating factors
Epoetins
Histone deacylating inhibitors
Hypomethylating agents
Iron
Iron chelating agents
Lenalidomide
Methotrexates
Platelets
Platelets Thalidomide

Non-response (to investigational product)

A non-responder is a subject who, after study day 35, received two transfusions that are \geq 21 days apart and \leq 42 days apart.

Objective tumor response rate (ORR)

The incidence of a complete or partial response at any time during the study. Response will be determined by the investigator's assessment of the scans using the version of RECIST specified in the protocol at the time of subject enrollment.

Overall survival (OS)

Time from randomization to date of death. Subjects will be censored on the date of last contact (ie, the date the subject was last known to be alive) if they are not known to be dead.

Progression-free survival (PFS)

Time from randomization to date of radiographic disease progression or death from any cause, whichever event occurs first. Subjects without either event will be censored on the date of their last disease assessment. Disease progression will be based on the investigator's assessment of scans using the version of RECIST specified in the protocol at the time of subject enrollment.

Rate of rise in hemoglobin >1.5 g/dL in 21 days

The occurrence of a hemoglobin that increases by >1.5 g/dL in any 21-day period in the treatment

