Unspecified/mixed thromboembolic events include thromboembolic events where the vessel type is either unspecified or a mix of arterial and venous. These events will be coded using MedDRA version **20.0** (or higher) and identified using the sub-SMQ 20000083 ("embolic and thrombotic events, vessel type unspecified and mixed arterial and venous") or more appropriate query available at the time of analysis.

Time to Progression (TTP)

Time from randomization to date of radiographic disease progression. Subjects without progression will be censored on the date of their last disease assessment. Disease progression will be based on the investigator's assessment of scans using the version of RECIST specified in the protocol at the time of subject enrollment.

Treatment Group

Subjects were randomized to 1 of 2 treatment groups: darbepoetin alfa (500 μ g) Q3W or placebo Q3W in a 2:1 allocation.

Treatment-emergent Adverse Event

A treatment-emergent adverse event is an adverse reported via the adverse event summary eCRF with an onset date between study day 1 and 30 days after the last dose of IP, inclusive, with one exception: VTEs and adverse events associated with RBC transfusions can have an onset date of 30 days after the last dose of IP or the EOTP visit, whichever is later.

6. Analysis Sets

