9.6.2 Secondary Safety Endpoint

The primary analysis of PFS will be based on the radiographic endpoint primary analysis set and will use a Cox regression model, stratified by the randomization factors, with treatment group as the only covariate. PFS will be measured from randomization to disease progression (as defined by the version of RECIST specified in the protocol at the time of subject enrollment) or death from any cause; subjects without either event will be censored at the last disease assessment date. If non-inferiority has been declared for OS, non-inferiority will be declared for PFS if the upper confidence limit for the hazard ratio is less than 1.15 using a 1-sided significance level of 0.025.

Sensitivity analyses for PFS will be done similar to those for the primary endpoint, OS, as further exploratory analyses for the secondary endpoint: However, the sensitivity analyses will be largely limited to the Radiographic Endpoint Primary Analysis Set (ie, few sensitivity analyses using the Per Protocol Analysis Set or any other data set are planned). In addition, a sensitivity analysis may be performed that examines the treatment effect by subgroups formed on the basis of which version of RECIST was used to evaluate the subject. If this analysis is performed, however, the results will need to be interpreted cautiously since the version of RECIST will be confounded with time of enrollment (RECIST 1.0 subjects will be enrolled first, RECIST 1.1 subjects second) and it is anticipated that less than 10% of the subjects will be evaluated with RECIST 1.0.

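### SAP 8.3.2 applies the TTP censoring rule to PFS as well and makes no exception for death, contrary to the plan's own PFS definition

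*SAP*

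**What the plan says.** SAP 8.3.2 (Missing Progression Data) states the rule in one sentence. The condition is "If radiographic disease progression is not observed, the primary analysis". The scope is "of progression-free survival and time to progression". The action is "will censor subjects at their last on-study disease assessment date". Death is not mentioned.

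The passages that define the endpoints read differently:

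- SAP Section 5 (Definitions), PFS: "Time from randomization to date of radiographic disease progression or death from any cause, whichever event occurs first". Only subjects with neither event are censored.
- SAP 9.6.2, primary analysis of PFS: the event is progression "or death from any cause; subjects without either event will be censored at the last disease assessment date".
- Protocol 10.6.2.2: progression is judged "using investigator-assessed scans) or death from any cause; subjects without either event will be censored at the last disease assessment date". The protocol synopsis gives the same rule.
- SAP Section 5, TTP: "Subjects without progression will be censored on the date of their last disease assessment".

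SAP Section 10, which lists changes from the protocol-specified analyses, does not mention any change to what counts as a PFS event.

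**The concern.** A subject who dies without progression on a scan is a PFS event under four passages and a censored observation under 8.3.2. Such deaths are foreseeable: a subject can die between scheduled scans, and protocol 7.5 lets subjects who cannot continue imaging move to long-term follow-up.

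PFS is the second step of the testing hierarchy in SAP 9.1. The transfusion test depends on it, and so do the later superiority tests. If 8.3.2 were programmed as written, PFS would in effect become TTP. The event and censored counts that the SAP 9.6 endpoint table calls for would be wrong, precision would fall, and the hazard ratio compared with the 1.15 margin would be that for progression alone.

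**Working it through.** **1. Text comparison.** Take one subject who dies with no radiographic progression.

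| Place | Condition for censoring | This subject's PFS status |
|---|---|---|
| SAP Section 5, PFS | neither progression nor death | event |
| SAP 9.6.2 | neither progression nor death | event |
| Protocol 10.6.2.2 and synopsis | neither progression nor death | event |
| SAP 8.3.2 | no radiographic progression | censored |

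Under the TTP definition in SAP Section 5 the same subject is censored. The 8.3.2 rule is therefore the TTP rule, extended to PFS by naming both endpoints.

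**2. Is there a planned figure to reproduce?** No. The documents give no PFS event count, no PFS power, and no share of PFS events that are deaths without scan progression. Call that share *f*. Everything below is an illustration over assumed values, f = 5%, 10%, 20% and 30%.

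**3. Precision.** The standard error of the log hazard ratio is proportional to 1/√events. If a fraction f of events is lost, the confidence interval widens by 1/√(1 − f) − 1:

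- f = 5%: 1/√0.95 − 1 = 2.6%
- f = 10%: 1/√0.90 − 1 = 5.4%
- f = 20%: 1/√0.80 − 1 = 11.8%
- f = 30%: 1/√0.70 − 1 = 19.5%

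This result does not depend on the total number of events.

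**4. Direction.** Assume constant cause-specific hazards, with f the share of the placebo-arm PFS hazard that is death without progression. The PFS hazard ratio under Section 5 is (1 − f) × HR_prog + f × HR_death. Under a literal 8.3.2 it is HR_prog alone.

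- *Equal effects:* HR_prog = HR_death, so the two rules give the same hazard ratio.
- *Excess only in deaths without progression:* with HR_prog = 1.0 and an assumed HR_death of 1.5, Section 5 gives 1 + 0.5f = 1.025, 1.05, 1.10 and 1.15 for the four shares. Literal 8.3.2 gives 1.00 each time. At f = 20%, assumed HR_death values of 1.15, 1.3, 1.5 and 2.0 give 1.03, 1.06, 1.10 and 1.20 under Section 5, again against 1.00.
- *Excess only in progression:* if Section 5 gives 1.15 with HR_death = 1.0, then HR_prog = 1 + 0.15/(1 − f) = 1.158, 1.167, 1.188 and 1.214. Literal 8.3.2 moves further from non-inferiority.

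The sign of the shift therefore depends on where any treatment effect lies, and the documents do not settle that.

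**The case against.** The best defence is that 8.3.2 sits under the handling of missing data. A subject who died without progression has an observed PFS event, so nothing is missing and the sentence was never meant to reach that subject. The defining passages agree with one another, and SAP 9.6.2 is the section that sets out the primary PFS analysis. Section 8.3 also abbreviates elsewhere. The survival rule in 8.3.1, "Subjects who did not die on study and are lost to follow-up will be censored on the date last known to be alive", covers only subjects lost to follow-up and leaves the complete OS censoring rule to Section 5. On this view a careful programmer would follow Section 5 and 9.6.2, and nothing would go wrong.

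Most of this stands. It shows that the intended endpoint is clear and that any effect on the result requires a literal reading of 8.3.2. It does not remove the conflict, because the sentence prescribes a censoring action for the primary analysis of PFS by name. The comparison with 8.3.1 also cuts both ways: that rule, although abbreviated, does condition on the subject not having died, and 8.3.2 does not.

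Two further limits are fair. PFS is tested only after OS non-inferiority is shown, and OS counts every death, so an excess of deaths without progression would first have to pass the OS test. And SAP 4.2 is no evidence on either side: its list of subjects unaffected by early closure includes withdrawn and lost subjects alongside deaths and progressions, so it does not define PFS events.

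**Conclusion.** The inconsistency is real and should be corrected. SAP 8.3.2 is right for TTP and wrong as written for PFS. It is a drafting error with a clear intended reading.

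Its effect on the trial result is unknown, and is nil if the programming follows Section 5 and 9.6.2. Under a literal reading, the loss of precision would be about 3% to 20% in the width of the log hazard ratio interval, on the assumption that 5% to 30% of PFS events are deaths without scan progression. The point estimate could move either way.

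A reader might infer two stronger conclusions. One is that the sponsor meant to drop death from PFS. The defining passages and the silence of Section 10 speak against that. The other is that the rule biases PFS toward non-inferiority or costs a definite amount of power. The documents do not support this either: they give no PFS event count, no planned PFS power and no share of such deaths, and the direction depends on whether any effect lies in progression or in death.

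**What to change.** In SAP 8.3.2, limit the existing sentence to time to progression. For PFS, write: *If neither radiographic disease progression nor death is observed, subjects will be censored at their last disease assessment date.*

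This restores what SAP Section 5, SAP 9.6.2 and protocol 10.6.2.2 already say. It costs one sentence, needs no new data and adds no analysis.
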